## **6 Treatment**

### **6.1 Patient numbering**

Each patient in the study is uniquely identified by a patient number which is a combination of his/her center number and subject number. The center number is assigned by Novartis to the investigative site. Upon signing the informed consent form, the patient is assigned a patient number by the investigator. At each site the first patient is assigned patient number 1, and subsequent patients are assigned consecutive numbers (e.g., the second patient is assigned patient number 2, the third patient is assigned patient number 3). Once assigned to a patient, a patient number will not be reused for any other patient. If the patient fails to enter the trial for any reason, the reason for not being enrolled to the trial will be entered on the Screening Log.

The patient list has to be kept separate from the other study documents and must not be transferred to the sponsor for any reason.

### **6.2 Investigational and control drugs**

Tobramycin, either as Tobramycin inhalation solution (TIS, 300mg/5mL or 300mg/4mL) to be nebulized or as Tobramycin inhalation powder (TIP, 112mg), as prescribed by the treating physician. Neither TIS nor TIP will be provided to the patient.

### **6.3 Treatment arms**

This is a single arm study including solely patients treated routinely with inhaled Tobramycin (study drug) in a 28 days on / off treatment regimen.

### **6.4 Treatment assignment**

All patients will continue their standard maintenance-therapy with Tobramycin inhalation (study drug) in a 28 days on / off cycle, as prescribed by the treating physician and in accordance with the SmPC.

### **6.5 Treatment blinding**

Not applicable. This study has an open-label design.

### **6.6 Treating the patient**

#### **6.6.1 Dispensing the study drug**

Patients will be treated by standard of care according to investigators' routine. Commercially available product will be used as prescribed by the treating physician.

#### **6.6.2 Instructions for use of study drug**

Study drug will be used according to the prescription of the treating physician, in a 28 on / off treatment regimen and in accordance with the SmPC.

#### **6.6.3 Study drug supply and resupply, storage, and tracking**

Medication will be stored by the patient following the guidance in the SmPC. Study drug will not be provided to the patient by Novartis.

#### **6.6.4 Study drug compliance and accountability**

##### **6.6.4.1 Study drug compliance**

In this study, patients will be treated by standard of care in investigators' routine dosing frequency. Compliance will be assessed by the investigator and/or study personnel at patient visit 3, 4 and, if needed, 5. Information provided by the patient will be captured in the source data and in the CRF. To support the patient in reporting his compliance at visits 3 and 4, a medication diary will be provided.

##### **6.6.4.2 Study drug accountability**

Not applicable. Study drug will not be provided to the patient.

#### **6.6.5 Disposal and destruction**

Not applicable. Study drug will not be provided to the patient.

### **6.6.6 Permitted study drug dose adjustments and interruptions**

Study drug dose adjustments are not permitted.

Any interruption of the inhalation of antipseudomonal antibiotics must be recorded on the Dosage Administration Record CRF. Discontinuation of study drug treatment for more than 3 days during the on treatment phase leads to premature study withdrawal.

### **6.6.7 Rescue medication**

Rescue medication is any on demand medication at acute clinical deterioration of the patient, independent of the currently used standard therapy. Short acting bronchodilators are allowed at any time, except 6 hours or less prior to each FEV1/Spirometry and LCI measurement. For other rescue medication or concomitant treatments to relieve symptoms of the underlying disease, see Section 6.6.8.

Drug and dose of used rescue medication must be recorded on the Concomitant medications/Significant non-drug therapies after start of study drug CRF.

### **6.6.8 Other concomitant treatment**

**If a patient experiences a pulmonary exacerbation and/or worsening the disease condition he/she will be treated as deemed appropriate by the investigator.** Following treatment for the Pulmonary exacerbation and/or worsening the condition, the patient will be expected to continue in the study if, in the opinion of the investigator, he/she can be safely returned to their pre-Pulmonary exacerbation concomitant medications. If the patient requires the prohibited treatment listed in Table 6-1, then he/she should be withdrawn from the study.

**Table 6-1 Prohibited treatment**

Medication	Action to be taken
Any inhaled antipseudomonal antibiotics other than tobramycin	Discontinue the study
Loop Diuretics	Discontinue the study
Any iv or oral antipseudomonal antibiotic 28 days prior baseline (V1) and 23 days prior end of study visit (V5)	Discontinue the study
Any other investigational treatments	Discontinue the study
Short Acting Beta Agonists (SABA)	Held treatment at least 6 hrs prior to each FEV1/Spirometry and LCI measurement.
Long Acting Beta Agonists (LABA) and	Held treatment at least 12 hrs prior to each

Long Acting Muscarinic Antagonists (LAMA)	FEV1/Spirometry and LCI measurement.
---	--------------------------------------

**Table 6-2 Washout of prohibited treatment and study treatment/concomitant medication prior to study visits**

Treatment/medication	Wash-out time	Timepoint	Remarks
SABA	6hours (h)	Prior to FEV1/LCI Assessment	
LABA / LAMA	12h	Prior to FEV1/LCI Assessment	
iv/oral Antibiotics	allowed in on-Phase + 5 Days in following off	Prior to Visit 5	Inhalation of Tobramycin stopped for more than 3 days: Discontinue the study
iv/oral Antibiotics	28 days	Prior to Visit 2	
Inhalation of Tobramycin	1h	Prior to FEV1/LCI Assessment	
Inhalation of Tobramycin	10h	Prior to sputum sampling (Sputum may be collected at home prior to visit)	Example for V3/4: Sputum sampling at home followed by Inhalation. Visit 4 on the next day.
Inhalation of Colistin or Aztreonam	56 days	Prior to visit 2	
Change in physiotherapy or inhalative concomitant medication, eg macrolides or steroids	56 days	Prior to visit 2	Macrolides, physiotherapy, pulmozyme, hypertonic saline, bronchitol, steroids, bronchodilators. Stable treatment is allowed.
Any other study drug	30 days	Prior to visit 1	30 days or 5x T 1/2, whichever is longer

The following treatments **are permitted** between start of the study drug administration and completion/termination and should be accurately documented in the CRF:

- Anti-pseudomonal antibiotics
  - Intravenous or oral Anti-pseudomonal antibiotics are allowed for the treatment of Pulmonary exacerbation during the on-phase as needed by patient condition if i.v. treatment is completed 5 days latest after the end of the on-phase.
  - If patients are prescribed i.v. aminoglycosides for symptoms of pulmonary exacerbation, continuation of inhalation of Study drug is at the investigator's discretion.
    - If inhalation of Study drug is continued during i.v. aminoglycoside therapy, patients will continue with the study schedule for the remainder of the study; however, therapeutic drug monitoring is strongly recommended with appropriate modification of the i.v. aminoglycoside dose as necessary;
    - Inhalation of antibiotics can be interrupted during i.v. aminoglycoside therapy (eg. due to elevated serum levels of study drug) for a maximum of 3 days. Patients should restart inhalation of antibiotics in order to complete the 28 days cycle as close as possible to their initial study schedule.
  - Pre-planned anti-pseudomonal antibiotics (i.v.) in the absence of an AE (prophylaxis of Pulmonary exacerbation) are not permitted during the study and 28 days prior Baseline Visit (V2)
- Macrolides (anti-inflammatory regimen)  
Patients should have been initiated or terminated on oral chronic macrolide therapy (i.e., macrolides prescribed for more than 14 days) more than 56 days (8 weeks) prior Baseline Visit (V2) and should remain on treatment or off treatment respectively through the completion/termination visit.
- Bronchodilators  
Patients should have been kept on the same regimen more than 56 days (8 weeks) prior to Baseline Visit (V2) through the completion/termination visit. If patients are taking short acting bronchodilators, they should have been inhaled 6 hours prior to any spirometric assessments or MBW measurement and long-acting bronchodilators should have been inhaled their last dose at least 12 hours prior to any spirometric or LCI assessments.
- Inhaled hypertonic saline  
Patients should have been initiated on therapy more than 56 days (8 weeks) prior Baseline Visit (V2) and should remain on unaltered treatment through the completion/termination visit. In addition, patients should be instructed to take their hypertonic saline at least 1 hour before their spirometric or LCI assessments. Patients should be consistent with the timing of taking their hypertonic saline at home or at the clinic prior to their spirometric or LCI assessments.
- Inhaled Mannitol

Patients should have been initiated on therapy more than 56 days (8 weeks) prior Baseline Visit (V2) and should remain on unaltered treatment through the completion/termination visit. In addition, patients should be instructed to take their mannitol at least 1 hour before their spirometric or LCI assessments. Patients should be consistent with the timing of taking their hypertonic saline at home or at clinic prior to their spirometric or LCI assessments.

- Dornase alfa

Patients should have been initiated on therapy more than 56 days (8 weeks) prior Baseline Visit (V2) and should remain on unaltered treatment through the completion/termination visit.

- Oral or Inhaled corticosteroids

Patients should have been initiated on therapy more than 56 days (8 weeks) prior to Baseline and should remain on unaltered treatment through the completion/termination visit.

- Use of oxygen, nutritional supplements, and enzymes is unrestricted at all times.

Use of all anti-pseudomonal antibiotics and macrolides administered within 12 months prior to screening will be recorded in the CRF.

The investigator should instruct the patient to notify the study site about any new medications he/she takes after the start of the study. All medications and significant non-drug therapies (including physical therapy and blood transfusions) administered after the patient was enrolled in the study must be documented in the source data and listed on the Concomitant medications/Significant non-drug therapies in the CRF.

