## Glossary of terms

Assessment	A procedure used to generate data required by the study
Control drug	A study drug used as a comparator to reduce assessment bias, preserve blinding of investigational drug, assess internal study validity, and/or evaluate comparative effects of the investigational drug
Enrollment	Point/time of patient entry into the study; the point at which informed consent must be obtained (i.e., prior to starting any of the procedures described in the protocol)
Investigational drug	The study drug whose properties are being tested in the study
Medication number	A unique identifier on the label of each study treatment package which is linked to one of the treatment groups of a study
Patient number	A number assigned to each patient who enrolls in the study; when combined with the center number, a unique identifier for each patient in the study is created.
Phase	A major subdivision of the study timeline; begins and ends with major study milestones such as enrollment, randomization, completion of treatment, etc.
Period	A minor subdivision of the study timeline; divides phases into smaller functional segments such as screening, baseline, titration, washout, etc.
Premature patient withdrawal	Point/time when the patient exits from the study prior to the planned completion of all study drug administration and assessments; at this time all study drug administration is discontinued and no further assessments are planned, unless the patient will be followed for progression and/or survival

Randomization number	A unique identifier assigned to each randomized patient, corresponding to a specific treatment arm assignment
Study drug	Any drug administered to the patient as part of the required study procedures; includes investigational drug, combination of drugs and any control drugs including placebo
Study drug discontinuation	Point/time when patient permanently stops taking study drug for any reason; may or may not also be the point/time of premature patient withdrawal
Variable	Information used in the data analysis; derived directly or indirectly from data collected using specified assessments at specified timepoints

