### **6.6.9 Study drug discontinuation**

Study drug must be discontinued for a given patient if the investigator determines that continuing it would result in a significant safety risk for that patient. The following laboratory abnormalities **require** study drug discontinuation:

- above-normal BUN (40mg/dl or greater) following an earlier result within the normal range
- above-normal creatinine (2mg/dl or greater) following an earlier result within the normal range

In addition, the study drug has to be discontinued on any sign of hypersensitivity against Tobramycin and on signs of oto- or nephrotoxicity. In case of oto- or nephrotoxicity, an assessment of Tobramycin serum level is recommended. If the level is fallen below 2 $\mu$ g/ml, a restart of study drug may be considered by the investigator. A therapeutic drug monitoring should be initiated in patients with a history of any renal dysfunction and study drug has to be discontinued if the Tobramycin serum level exceeds 12 $\mu$ g/ml.

The last date of study drug intake should be entered into the Study Completion CRF and the reason for discontinuing study drug should be given on the comments page. If a patient who discontinued study drug therapy performed all scheduled study procedures and measurements, he will be counted as a study completer.

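### Protocol rules for stopping, restarting and withdrawing after tobramycin toxicity or a raised serum level contradict each other in three specific overlaps

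*Protocol*

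**What the plan says.** **Interruption during i.v. aminoglycosides.** Protocol section 6.6.8, in the list of permitted treatments after Table 6-2, first states that "continuation of inhalation of Study drug is at the investigator's discretion". It then sets the limit: "Inhalation of antibiotics can be interrupted during i.v. aminoglycoside therapy (eg. due to elevated serum levels of study drug) for a maximum of 3 days". The next sentence expects a return to drug: "Patients should restart inhalation of antibiotics in order to complete the 28 days cycle as close as possible to their initial study schedule". No serum level is attached to the interruption or to the restart.

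**Mandatory stop.** Protocol section 6.6.9 states that "the study drug has to be discontinued on any sign of hypersensitivity against Tobramycin and on signs of oto- or nephrotoxicity". For oto- or nephrotoxicity it recommends measuring the serum level and adds that, once the level is below 2 µg/ml, "a restart of study drug may be considered by the investigator". No time limit is given. A further sentence, on patients with a history of renal dysfunction, says that "study drug has to be discontinued if the Tobramycin serum level exceeds 12" µg/ml and mentions no restart. The section ends by counting as a study completer any patient who stopped the drug but performed all scheduled procedures.

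**Withdrawal.** Protocol section 6.6.6: "Discontinuation of study drug treatment for more than 3 days during the on treatment phase leads to premature study withdrawal". Section 5.2 lists the same condition among the reasons for mandatory withdrawal. Table 6-2 repeats it as a remark in the row on i.v. and oral antibiotics. None of the three makes an exception for toxicity.

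**Definition and follow-up.** The glossary defines study drug discontinuation as: "Point/time when patient permanently stops taking study drug for any reason". It adds that this may or may not coincide with withdrawal from the study. Section 7 brings patients who discontinue the drug, as well as those who withdraw, to an early visit with the final-visit assessments.

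**The concern.** Several passages apply to the same patient and can give different answers. After a sign of toxicity, a site needs to know whether the stop is temporary or permanent, whether a restart is still open after three days, and whether the patient stays on the visit schedule. The protocol answers these questions differently in different sections.

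The SAP foresees these events. Section 2.8.1.1 names elevated BUN and creatinine, tinnitus and hearing loss as events of special interest, and tabulates events leading to permanent discontinuation of study drug. SAP section 2.3.1 counts completers, study discontinuations and treatment discontinuations separately. These tables depend on terms that the protocol does not use consistently. Missing Week 4 data are not imputed (SAP section 2.5.3), and withdrawn patients are not replaced (Protocol section 5.2). The passage that is followed therefore also decides whether scheduled Week 4 and Week 8 LCI values exist for that patient.

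**Working it through.** **Figures available.** The documents give no expected number of patients with toxicity or raised levels, so no effect on the trial can be calculated. The only related figure is the sample size (Protocol section 10.7). A paired t-test with a change of 5 and an SD of the change of 9, at two-sided 5%, gives n = 28 with power 0.809, which reproduces the plan's 28. At the target of 35 the power is 0.891, and 35 − 28 = 7 losses are allowed for. These figures concern FEV1 and are background only.

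**Overlap 1: restart against permanence and the 3-day rule.** Let *d* be the first on-phase day without drug and *r* the day of restart, counting whole days.

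- Days off drug = *r* − *d*. The withdrawal rule is met if more than 3 of these fall in the on-phase.
- With an on-phase of Days 1 to 28, the days that can be missed number 29 − *d*. This exceeds 3 only if *d* ≤ 25. A stop that begins on Day 26 or later cannot trigger the rule.
- For *d* ≤ 25, a restart at *r* ≤ *d* + 3 satisfies both sections 6.6.9 and 5.2. From *r* = *d* + 4, section 6.6.9 still permits restart, while sections 5.2 and 6.6.6 already require withdrawal.

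Illustration (both days assumed): the first day without drug is Day 8, and the level falls below 2 µg/ml on Day 13. Then 13 − 8 = 5, which exceeds 3, and the fourth day off drug is Day 11. Under section 6.6.9 alone the patient may restart on Day 13 and attend Week 4 (Days 25 to 28) and Week 8 (Days 53 to 56). Under sections 5.2 and 6.6.6 the patient has already been withdrawn.

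The glossary adds a separate conflict. If discontinuation is permanent, neither the restart in section 6.6.9 nor a discontinuation lasting a number of days, as in sections 5.2 and 6.6.6, has a clear meaning.

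**Overlap 2: completer against withdrawn.** A permanent stop with *d* ≤ 25 always accumulates at least 29 − 25 = 4 on-phase days off drug, so sections 5.2 and 6.6.6 withdraw the patient. Read literally, the completer sentence in section 6.6.9 can then apply only to on-phase stops starting on Days 26 to 28. Section 7 calls even those patients to an early final visit, although the completer sentence presupposes that all scheduled procedures are done.

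**Overlap 3: interrupt against stop at one serum level.**

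| | Section 6.6.8 | Section 6.6.9 |
|---|---|---|
| Applies to | Patients on i.v. aminoglycosides | Sentence on patients with a history of renal dysfunction |
| Trigger | Elevated level, no threshold | Above 12 µg/ml |
| Action | May interrupt, up to 3 days | Must discontinue |
| Restart | Expected, no level condition | Not mentioned |

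A patient with all three features (renal history, i.v. aminoglycoside, level above 12 µg/ml) falls in both columns. No threshold or order of precedence separates them.

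**Effect on the analysis.** Population membership does not change. The Safety set needs only consent and one dose (SAP section 2.2), and more than 3 days of interruption is deviation COMD06 with code 0 (SAP section 5.5). The model in SAP section 5.4.1 uses whatever values are observed at Visits 2 to 5. What can change is the completer or withdrawn status and the presence of scheduled Week 4 and Week 8 values.

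**The case against.** The strongest reply is that most of this text is coherent. The 3-day maximum in section 6.6.8 matches the withdrawal threshold. Stopping for toxicity and restarting at a low level is one sequence, and it fits the 3-day rule when the restart is prompt. The triggers differ, and the third overlap needs several conditions at once. A mandatory rule in section 6.6.9 would naturally be read as overriding a permissive one in section 6.6.8. The protocol also uses the word discontinuation loosely, so the explicit restart sentence makes its local meaning plain.

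Much of this stands, and it rules out several stronger readings that a reader might infer:

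- That all the instructions are mutually incompatible. They are not, for the reasons just given.
- That restart under section 6.6.9 requires the toxicity sign to resolve within 3 days. The section sets no such condition.
- That the recommended adjustment of the i.v. dose in section 6.6.8 contradicts the stop of the inhaled drug. Both can be done.
- That sites do act differently, or that the 3-day limit encourages early restart. Neither is shown. Tobramycin is the patient's own prescribed therapy and is not supplied by the sponsor, and section 5.2 provides for withdrawal in the patient's best interest.
- That 2.9% of the primary data is lost per patient. Visits already observed remain in the model, and final-visit assessments are to be done early.

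What the reply does not remove is the restart without a time limit beside a withdrawal rule without exceptions, the completer sentence beside mandatory withdrawal, and the absence of a stated precedence between sections 6.6.8 and 6.6.9.

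**Conclusion.** The contradiction holds in the three overlaps and no further. The first two do not depend on the narrow renal case. The consequences are how the patient is managed, whether the patient counts as a completer or as withdrawn, and whether scheduled Week 4 and Week 8 values exist.

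The size cannot be estimated. One patient is 1/35 = 2.9% of the planned sample, which is a scale and not an expected loss. The day counts assume whole-day counting and a 28-day on-phase starting on Day 1. The Day 8 to Day 13 example is assumed. No judgement is made on which clinical rule is right.

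**What to change.** Reconcile Protocol sections 5.2, 6.6.6, 6.6.8 (with Table 6-2), 6.6.9 and 7 and the glossary, preferably in one table. For each event (sign of oto- or nephrotoxicity, serum level above the stated limit, i.v. aminoglycoside use), the table should state:

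- one action, named as temporary interruption or permanent discontinuation and used as the glossary defines it;
- the restart condition, if any;
- whether the 3-day withdrawal rule applies;
- whether the patient stays on the visit schedule and counts as a completer.

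Where two events coincide, it should say which entry takes precedence. The clinical team chooses the content. The SAP disposition and discontinuation tables should then use the same terms. The cost is amendment wording and its approval, with no added visits, tests or patients.

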#### **6.6.8.1 Caution for concomitant use**

Based on the interaction profile for tobramycin following intravenous and aerosolized administration, concurrent and/or sequential use of Study drug with other drugs with neurotoxic, nephrotoxic, or ototoxic potential should be avoided.

Other medicinal products that have been reported to increase the potential toxicity of parenterally administered aminoglycosides include:

- amphotericin B, ceftazidime, cilostazol, cyclosporine, tacrolimus, polymyxins (risk of increased nephrotoxicity);
- platinum compounds (risk of increased nephrotoxicity and ototoxicity);
- anticholinesterases, botulinum toxin (neuromuscular effects).

Continuation of inhalation of Tobramycin or concomitant use of these substances is at the investigator's discretion. A close monitoring is strongly recommended

